## 4. Study Treatment

### 4.1 Study Drug Dosage and Administration

The first five (5) subjects enrolled will comprise the Sentinel Group. After all subjects in the Sentinel Group have successfully completed Day 99 (14 weeks) of the study, and the DMC has reviewed the accumulated data and given approval for enrollment of the Core Group to proceed, subjects six (6) through twenty (20) will be enrolled.

For the IV administrations (IVI and IV push), study drug will be administered intravenously via a 23-gauge IV butterfly. Study drug should be administered in the cephalic vein of the subject's right or left arm. If this vein is not accessible, an appropriate vein located elsewhere can be used. The administration site will be recorded in the source documents and CRF. Once placed, the IV line should be flushed with 2-5 mL of saline to insure proper placement. Study drug administration by IV infusion, bolus, or push should be done as per the protocol. Once drug administration is completed the line should be flushed with 2-5 mL of normal saline prior to removal of the device. An infusion pump (like Baxter Flo Gard 6201, Bodyguard 323 CME, or similar – not supplied by the Sponsor) should be employed as needed to achieve study drug administration times indicated in the protocol for IVI and IV bolus. IV push dosing over 30 seconds should not be performed with a pump.

For the IM injections, a volume of 5.32 mL, corresponding to 800 mg Trogarzo®, will be administered over two injections of about 2.66 mL each. The two IM injections should be administered in the muscle tissue of the subject's anterolateral aspect of the thighs (left, right, or both). The two IM injections are to be administered in one body area and injection sites should be at least 1 inch apart. If an alternative body area is necessary for subject comfort/convenience, IM injections can be administered in the dorsogluteal site (upper outer quadrant of the buttock). Every effort should be made to limit injection sites to one body area for each dose, if possible. The injection site must be examined at baseline and described in detail for subsequent exam. This information will be recorded.

After sterilization of the injection site with an alcohol swab, the study drug will be injected using a syringe with a needle of appropriate gauge and length into the IM tissue. Injection site, body mass

index (BMI), needle gauge and length used will be collected in the eCRF. In brief, skin at the injection site will be stretched firmly and the study drug will be injected slowly into muscle tissue at a 90-degree angle.

### **All Subjects at Day 1/Baseline and Day 15**

At the Day 1/Baseline and Day 15 visits, all subjects in the study will receive a maintenance dose of 800 mg Trogarzo® diluted in 250 mL normal saline (at 3.2 mg/mL) and administered as an IVI over 15 minutes in accordance with the approved Trogarzo® prescribing information.

### **Sentinel Group (Subjects 1 to 5) at Day 29 (4 weeks) through Day 85 (12 weeks)**

Beginning at Day 29 and continuing through Day 85 (12 weeks), the 800 mg maintenance doses of Trogarzo® will be administered in the Sentinel Group at sequentially increasing concentrations and over sequentially reduced time periods in accordance with the study schedule (see Section [3.1](#) and [Table 1](#)). The sequential changes in the dilution and dosing rate in the Sentinel Group is as follows:

- Day 29 (4 weeks): 800 mg diluted in 50 mL normal saline (at 16 mg/mL) via IVI over 10 minutes
- Day 43 (6 weeks): 800 mg diluted in 16 mL normal saline (at 50 mg/mL) via IV bolus over 5 minutes
- Day 57 (8 weeks): 800 mg diluted in 8 mL normal saline (at 100 mg/mL) via IV bolus over 1 minute
- Day 71 (10 weeks): 800 mg undiluted (at 150 mg/mL) via IV push over 30 seconds
- Day 85 (12 weeks): 800 mg undiluted (at 150 mg/mL) via IV push over 30 seconds

When five (5) subjects in the Sentinel Group have completed Day 99 (14 weeks) of the study, the DMC will review the available data to determine whether the enrollment of the Core Group should proceed.

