Administer study drug – reducing administration time and increasing study drug concentration in step-wise fashion at each visit per schedule 										X		X		X	

	Study Visit														
	Screening	Day 1 Baseline	Day 2	Day 4	Day 8 (1 wk)	Day 15 (2 wks)	Day 16	Day 18	Day 22 (3 wks)	Day 29 (4 wks)	Day 36 (5 wks)	Day 43 (6 wks)	Day 50 (7 wks)	Day 57 (8 wks)	Day 64 (9 wks)
Visit window (days)	(-28 days)	N/A	±3 hr	±3 hr	±1	±1	±3 hr	±3 hr	±1	±1	±1	±1	±1	±1	±1
Observe subject for 15 minutes post-administration; record vital sign measurements after completion of infusion and again at end of observation period 		X				X				X		X		X	

 All ART for the 3 months preceding Screening will be recorded at Screening visit; subsequent visits will only record changes to ART.

 Abbreviated physical examination includes examination of lymph nodes, respiratory and cardiovascular systems, abdomen, extremities, and nervous system.

 Only record AEs that are related to study procedures before administration of the first dose.

 Subjects do not need to fast before blood sampling.

 Serum FSH test to be conducted on postmenopausal females at Screening only.

 Pre-dose samples to be collected within 1 hour before the start of the infusion; 24 hr, 72 hr, and 7 Day post dose samples to be collected within 3 hours of the time the infusion ended.

 At Baseline and at Day 15 all subjects in the Sentinel Group (the first 5 subjects enrolled) will receive study drug diluted into 250 mL normal saline as a standard 800 mg IV infusion over 15 minutes, per Trogarzo® prescribing information. At Day 29, Sentinel Group subjects will begin receiving Trogarzo® 800 mg at increasing concentrations over decreasing intervals as follows: Day 29 (4 weeks) – 16 mg/mL delivered over 10 minutes (800 mg study drug diluted into 50 mL normal saline); Day 43 (6 weeks) – 50 mg/mL delivered over 5 minutes (800 mg study drug diluted into 16 mL normal saline); Day 57 (8 weeks) – 100 mg/mL delivered over 1 minute (800 mg study drug diluted into 8 mL normal saline). All subjects must be observed for 15 minutes after the completion of each study drug administration. Vital signs should be monitored and recorded at the beginning and end of the observation period.

 Any abnormalities observed need to be recorded on the AE CRF.

Schedule of Events – Sentinel Group (Subjects 1-5) (CONTINUED)

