## 4.3 Safety Monitoring and Toxicity Management Plan

### Sentinel Group

This trial will employ a sentinel group of 5 subjects to determine the safety of progressively shortening the administration time while increasing the drug concentration of Trogarzo® with the goal of delivering an 800 mg dose (5.32 mL at 150 mg/mL) via IV push over 30 seconds.

A dose-limiting toxicity (DLT) will be defined as:

- Any Grade 3 or greater toxicity that the study investigators recognize as probably or definitely attributable to Trogarzo® administration. Grade 3 and 4 laboratory abnormalities must be confirmed by a repeat test obtained as soon as possible following the initial result

OR

- Any subject with Grade 2 infusion-related reaction and/or cytokine release syndrome (see [Appendix B – DAIDS Grading Table V2.1](#) for cytokine release syndrome).

**The first 2 subjects in the Sentinel Group will be enrolled and treated at least 2 weeks prior to the enrollment and treatment of the remaining 3 subjects.**

If no DLT occurs within 7 days of Trogarzo® shortened IV infusion, bolus, or push administration then dosing of additional subjects may continue with approval of the DMC.

If 1 DLT occurs within 7 days of Trogarzo® dosing at a shortened IV infusion, bolus, or push administration then the DMC should be notified; however, dosing may continue. The individual experiencing the DLT should resume dosing as per current FDA-approved administration instructions and the subject will discontinue from the study.

If 2 DLTs occur within 7 days of Trogarzo® dosing at a shortened IV infusion, bolus, or push administration then such administration should be suspended and further dosing of Trogarzo® should resume as per current FDA-approved administration instructions.

Any SAE deemed related to the change in administration time and concentration of Trogarzo® in any participant in the Sentinel Group will result in cessation of dosing at increased concentration and over intervals <15 minutes. The DMC should review the event and all scheduled Trogarzo® dosing should resume as per current FDA-approved administration instructions to avoid loss of virologic control. The DMC may recommend resumption of the Sentinel Group dosing schedule after review of the SAE.

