## 4.5 Study Drug Description

HIV-infected study participants will be treated with commercially packaged Trogarzo® according to the instructions for infusion in the approved prescribing information both prior to and after completion of this study. HIV-uninfected healthy volunteers will be treated with drug packaged and labeled for clinical research use provided to study sites by the study sponsor.

To prevent potential loss of benefits and disruption of drug availability to the HIV-infected participants, study drug will be obtained at the clinical sites using the same means for obtaining the commercial drug employed for that subject prior to study entry and after study completion. Thus, investigators will be asked to apply labels to the TMB-302 study drug as required for an Investigational New Drug Application (IND) study utilizing labels and procedures provided by the Sponsor or Designee.

Trogarzo® is a single-use parenteral formulation contained in a 2 mL, clear-glass vial, and packaged into cartons containing 2 vials each. The drug product contains ibalizumab-uiyk at a concentration of 150 mg/mL, histidine United States Pharmacopoeia (USP), sucrose, sodium chloride, polysorbate 80, and water for injection USP at pH 6.0. Each vial contains at least 1.33~ mL of fluid delivering a

total of 200 mg study drug per vial. Each 800 mg dose of study drug will thus require 4 vials (2 cartons for HIV-infected and 4 cartons for HIV-uninfected due to differences in packaging) of Trogarzo®. The stability of Trogarzo® at 2°C to 8°C is evaluated in ongoing studies. For any period of storage, Trogarzo® must be under refrigerated conditions with a temperature-monitoring device. Trogarzo® should be maintained at 2°C to 8°C (but NOT FROZEN) and protected from light in accordance with Trogarzo® packaging information.

Any spent vials or remaining contents of used vials should be destroyed according to the site's procedures for spent vial destruction and disposal only after complete drug accountability records have been reviewed and accepted during routine monitoring, and written permission has been given for spent vial destruction. The destruction should be documented.

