#### Sentinel Group

Subjects in the Sentinel Group will receive an 800 mg maintenance dose of Trogarzo® in accordance with the prescribing information (diluted in 250 mL normal saline and administered over 15 minutes via IV infusion) at Day 1/Baseline and again at Day 15. Every two weeks thereafter through Day 85 (12 weeks), subsequent maintenance doses

will be administered at increasing concentrations and over decreasing intervals according to the following schedule:

- Day 1/Baseline: 800 mg diluted in 250 mL normal saline (at 3.2 mg/mL) via IV Infusion over 15 minutes per approved Trogarzo® prescribing information
- Day 15 (2 weeks): 800 mg diluted in 250 mL normal saline (at 3.2 mg/mL) via IV Infusion over 15 minutes per approved Trogarzo® prescribing information
- Day 29 (4 weeks): 800 mg diluted in 50 mL normal saline (at 16 mg/mL) via IV Infusion over 10 minutes
- Day 43 (6 weeks): 800 mg diluted in 16 mL normal saline (at 50 mg/mL) via IV Bolus over 5 minutes
- Day 57 (8 weeks): 800 mg diluted in 8 mL normal saline (at 100 mg/mL) via IV Bolus over 1 minute
- Day 71 (10 weeks): 800 mg undiluted (at 150 mg/mL) via IV push over 30 seconds
- Day 85 (12 weeks): 800 mg undiluted (at 150 mg/mL) via IV push over 30 seconds
- Day 99 (14 weeks), End of Study (EOS) visit: 800 mg diluted in 250 mL normal saline (at 3.2 mg/mL) via IV Infusion over 15 minutes per approved Trogarzo® prescribing information

Core Group: HIV-infected subjects

After DMC review and approval, the Core Group (subject numbers six (6) through twenty (20)) will be enrolled. Subjects in the Core Group will also receive an 800 mg maintenance dose of Trogarzo® in accordance with the prescribing information (diluted in 250 mL normal saline and administered over 15 minutes via IV infusion) at Day 1/Baseline and again at Day 15. Every two weeks thereafter through Day 71 (10 weeks), maintenance doses will be administered via undiluted IV push over 30 seconds. At Day 84 (12 weeks), Core Group subjects will revert to diluted IV infusion dosing over 15 minutes in accordance with the Trogarzo® prescribing information.

- Day 1/Baseline: 800 mg diluted in 250 mL normal saline (at 3.2 mg/mL) via IV Infusion over 15 minutes per approved Trogarzo® prescribing information
- Day 15 (2 weeks): 800 mg diluted in 250 mL normal saline (at 3.2 mg/mL) via IV Infusion over 15 minutes per approved Trogarzo® prescribing information
- Day 29 (4 weeks): 800 mg undiluted (at 150 mg/mL) via IV push over 30 seconds

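### Read literally, the Sentinel dilution volumes contradict their stated concentrations (about 14.5, 37.5 and 60 mg/mL against 16, 50 and 100), and neither document says whether the volumes are added saline or final volume.

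*Protocol*

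**What the plan says.** Protocol Section 4.1 sets out the Sentinel steps:

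- Days 1 and 15: 800 mg in 250 mL, stated as 3.2 mg/mL, over 15 minutes.
- Day 29: "800 mg diluted in 50 mL normal saline (at 16 mg/mL) via IVI over 10 minutes".
- Day 43: "800 mg diluted in 16 mL normal saline (at 50 mg/mL) via IV bolus over 5 minutes".
- Day 57: "800 mg diluted in 8 mL normal saline (at 100 mg/mL) via IV bolus over 1 minute".
- Days 71 and 85: undiluted drug at 150 mg/mL, pushed over 30 seconds.

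The same volumes and concentrations appear in the Synopsis (Study Design), in Section 3.1 and in Section 2.1 of the IV push SAP, for example "800 mg diluted in 16 mL normal saline (at 50 mg/mL) via IV Bolus over 5 minutes". Footnote 7 of protocol Table 1 uses the preposition *into*: "100 mg/mL delivered over 1 minute (800 mg study drug diluted into 8 mL normal saline".

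On the drug itself, Section 4.5 says "The drug product contains ibalizumab-uiyk at a concentration of 150 mg/mL". Section 4.3 gives the volume of one dose when it describes "the goal of delivering an 800 mg dose (5.32 mL at 150 mg/mL) via IV push over 30 seconds". The IM text in Sections 3.1 and 4.1 uses the same 5.32 mL.

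Nothing in either document says whether the listed volume is the saline to which the drug is added or the total volume of the finished preparation. The accountability records in Section 4.6 cover lot, expiry, preparation time and duration of administration. They do not cover diluent volume or final concentration.

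**The concern.** Each instruction names a volume of normal saline and a concentration. With more than 5 mL of drug in every dose, 8 mL of added saline and 100 mg/mL cannot both hold. Nor can 16 mL of added saline and 50 mg/mL. The discrepancy is negligible at 250 mL but grows as the diluent shrinks, so it is largest at the steps closest to the undiluted push.

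Concentration is one of the two things the Sentinel Group escalates; administration time is the other. Section 4.4 asks the DMC to judge whether a toxicity was caused by the faster rate, the higher concentration, or both. If the Day 57 preparation could have been 60 or 100 mg/mL, the concentration half of that judgement rests on an uncertain figure. With five Sentinel subjects and about 7 to 8 sites planned for the study, preparation could also differ between subjects.

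**Working it through.** Inputs: dose 800 mg; listed volumes 250, 50, 16 and 8 mL with their stated concentrations (Section 4.1); drug product 150 mg/mL (Section 4.5); drug volume per dose 5.32 mL (Section 4.3), which agrees with 800 / 150 = 5.33 mL.

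**The plan's own figures.** Taking the listed volume V as the final volume, concentration = 800 / V: 800/250 = 3.2, 800/50 = 16, 800/16 = 50 and 800/8 = 100 mg/mL. All four stated concentrations are reproduced exactly.

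**The literal reading.** Taking V as saline to which the drug is added, concentration = 800 / (V + 5.33).

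| Step | Listed volume (mL) | Stated mg/mL | Added-saline mg/mL | Shortfall |
|---|---|---|---|---|
| Days 1, 15 | 250 | 3.2 | 800/255.33 = 3.13 | 2% |
| Day 29 | 50 | 16 | 800/55.33 = 14.46 | 10% |
| Day 43 | 16 | 50 | 800/21.33 = 37.5 | 25% |
| Day 57 | 8 | 100 | 800/13.33 = 60.0 | 40% |
| Days 71, 85 | none | 150 | 150 | 0% |

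Using 5.32 mL instead of 5.33 changes the Day 43 and Day 57 results only to 37.52 and 60.06 mg/mL.

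**Fold increase from one step to the next.**

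- As stated: 5.0, 3.1, 2.0, then 150/100 = 1.5.
- Added saline: 4.6, 2.6, 1.6, then 150/60 = 2.5.

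**Saline needed if the stated concentration is the final one** (V minus 5.33): 44.7 mL at Day 29, 10.7 mL at Day 43 and 2.7 mL at Day 57.

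**Volume per minute around the last step.** Day 57 is 8 mL/min on the final-volume reading and 13.3 mL/min on the added-saline reading. The push is 5.33 mL in half a minute, or 10.7 mL/min. Volume rate therefore rises at the last step on one reading and falls on the other.

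**What does not change.** Drug delivered per minute is the same on both readings: 800/10 = 80, 800/5 = 160, 800/1 = 800 and 800/0.5 = 1,600 mg/min for Day 29, Day 43, Day 57 and the push.

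**The case against.** The strongest reply is that there is no arithmetic error. Every stated concentration is 800 mg divided by the listed volume, so the figures agree if that volume is the final volume. The concentration is printed at every step, and Table 1 footnote 7 puts it first. This stands, and it rules out saying flatly that the volumes are wrong. It does not remove the conflict, because the text names a volume of normal saline and nowhere calls it a final volume.

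The consequences are also limited:

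- Each Sentinel subject is due two undiluted pushes, on Days 71 and 85, and the DMC reviews the group after Day 99. The push is therefore observed directly before any Core subject is enrolled.
- The Sentinel DLT rules in Section 4.3 are triggered by any shortened infusion, bolus or push, not by a mg/mL figure.
- The PK comparisons are between the 15-minute infusion and the 30-second push. The Sentinel AUC intervals in the footnote to Listing 16.2.5.2 start on Days 1, 15, 71 and 85, so none covers the Day 29, 43 or 57 dose.

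These points stand and bound the issue.

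Two stronger inferences are tempting but unsupported. A reader might infer that the largest concentration jump falls at the first undiluted dose. In fold terms it does not: on the added-saline reading, 2.5 ranks third of the four steps. It is the largest in absolute terms (60 to 150, or +90 mg/mL), but on the stated figures the last step is already joint largest (+50, equal to the step from 50 to 100). A reader might also infer that the DMC reviewed a step mislabelled as 100 mg/mL. No DMC package is in the documents, and the IV push SAP mock tables label Sentinel periods by route and duration.

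**Conclusion.** The point holds as an unresolved conflict in the preparation instructions. On the literal reading, the Day 29, 43 and 57 concentrations fall short of their stated values by 10%, 25% and 40%. On the final-volume reading they are correct. The documents do not say which reading governs, so the 2.5-fold last step and the 13.3 mL bolus are conditional on the added-saline reading.

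The calculation assumes that drug and saline volumes add, that the full 5.33 mL is used, and that no saline is withdrawn to make room for it. Any preparation instructions outside these two documents could settle the matter, but none was available to check.

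This is more than a missing detail, because the affected group exists to escalate concentration safely. It does not affect the dose in mg, the mg per minute or the PK bridge. No view is taken on which preparation is right.

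**What to change.** Reconcile the Sentinel steps in the protocol Synopsis, Section 3.1, Section 4.1 and Table 1 footnote 7, and in Section 2.1 of the IV push SAP. For each step, state the drug volume, the diluent volume and the final volume, so that the mg/mL figure equals 800 mg divided by the final volume. The choice of preparation is for the sponsor.

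Sentinel dosing may already be finished. This is an inference: protocol Section 9.8 cites preliminary data from this study, and new IM subjects are recruited only after the Core Group completes. In that case, the report should give the concentration actually prepared at each step for each subject. Listing 16.2.4.1 in the IV push listings has starting and ending volumes, and a Day 57 starting volume near 8 mL or near 13.3 mL would distinguish the two readings. If preparation differed between subjects, the report should say so.

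The cost is wording in the protocol, the SAP and any pharmacy instructions, plus a check of existing records. No added subjects, visits or samples are needed.

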### **Core Group (Subjects 6 to 20) at Day 29 (4 weeks) through Day 71 (10 weeks)**

After DMC review of data from the Sentinel Group and approval obtained for the study to proceed, the Core Group (subject numbers six (6) through twenty [20]) will be enrolled. Beginning at Day 29 and continuing through Day 71 (10 weeks), subjects in the Core Group will receive an 800 mg maintenance dose q2wk as undiluted drug over 30 seconds.

In HIV-infected individuals, at Day 99 (14 weeks) for the Sentinel Group, and at Day 85 (12 weeks) for the Core Group, subjects will revert to receiving Trogarzo® as a diluted IVI over 15 minutes in accordance with the prescribing information.

In HIV-uninfected individuals Trogarzo® will be discontinued after the Day 71 IV push.

At Day 113 (16 weeks) for the Sentinel Group, and Day 99 (14 weeks) for the Core Group, only safety follow-up is performed. These visits may be performed via telephone if evaluation does not require a clinic visit, and subjects should return to routine administration of Trogarzo® through their primary care provider at this time point.

**IM Group (Subjects 21-40) at Day 29 (4 weeks) through Day 71 (10 weeks)**

Subjects in the IM Group will receive the first two doses of study drug in accordance with the Trogarzo® prescribing information (diluted in normal saline and administered over 15 minutes via IVI). The next four doses will be administered as an IM injection. At Day 85 (12 weeks), IM Group HIV-infected subjects will revert to diluted IVI dosing over 15 minutes in accordance with the Trogarzo® prescribing information.

In HIV-uninfected individuals Trogarzo® will be discontinued after the Day 71 injection.

Subjects will be followed for safety through 28 days after the last Trogarzo® administration on study (from Day 85 [12 weeks] through Day 113 [16 weeks] for the Sentinel and HIV-infected IM Groups, from Day 71 [10 weeks] through Day 99 [14 weeks] for HIV-uninfected Core and IM Groups , and at Day 99 for the HIV-infected Core Group). Safety follow-up visits may be performed via telephone if evaluation does not require a clinic visit, and subjects should return to routine administration of Trogarzo® through their primary care provider at this time point.

All subjects will be observed after completion of each study drug administration – 15 minutes if HIV-infected, 60 minutes if HIV-uninfected. In addition to noting any general acute reactions, the site of injection will be inspected, and any unusual signs noted. Vital signs will be recorded immediately after completion of study drug administration and again at the end of the observation period. All AEs occurring during observation will be recorded.

